PROTOCOL NAME: Epicenters for the Prevention of Healthcare Associated Infections (HAIs) -- Volume of Contamination and Nosocomial Infection Control: Specific Aim II.1 [Use of Providine to Protect HCW Hands (Aim II.1)]

PROTOCOL NUMBER:

Modification #: 0

PROTOCOL VERSION DATE: 10/20/2015

GENERAL INFORMATION

Name and address of the study monitor and person authorized to sign the protocol and amendments:

[name]

UIHC Research Team:

[name]

[name]

[name]

Name and addresses of the study site:

The University of Iowa Hospitals and Clinics

[name]

[name]

Table of Contents

SUMMARY	4
1. BACKGROUND INFORMATION AND RATIONALE	5
1.1. BACKGROUND INFORMATION	5
1.2. RATIONALE	5
1.3. RISKS	6
1.4. BENEFITS	6
1.5. RISK BENEFITS RATIO	6
2. STUDY OBJECTIVES	6
3. STUDY DESIGN AND PROCEDURES	6
4. SELECTION AND WITHDRAWAL OF PARTICIPANTS	8
4.1. SELECTION OF STUDY POPULATION	8
4.2. INCLUSION CRITERIA	8
4.3. EXCLUSION CRITERIA	8
4.4. PARTICIPANT WITHDRAWAL	8
5. INFORMED CONSENT PROCESS	8
5.1. RECRUITMENT	8

5.2.	ALTERATION OF CONSENT	9
5.3.	WAIVER OF HIPAA AUTHORIZATION	9
5.4.	INFORMED CONSENT PROCESS	9
6.	STATISTICAL PLAN	10
6.1.	ANALYSIS PLAN	10
6.2.	SAMPLE SIZE ESTIMATES	11
7.	DATA COLLECTION, HANDLING, AND STORAGE	12

Summary

This study seeks to investigate whether applying Provodine™ to hands protects against self-contamination during personal protective equipment (PPE) removal.

For centuries, HCWs have used special clothing and equipment to protect themselves when caring for patients with infectious diseases. Yet, we still lack basic information about the efficacy of most PPE items, the optimal removal (doffing) procedures, and the methods for educating staff and assessing their competence.(54) Recent outbreaks of severe acute respiratory syndrome (SARS), 2009 H1N1 influenza, and Ebola highlighted these deficiencies.(1, 12, 13, 55-60) Unfortunately, lessons learned from outbreaks of SARS and 2009 H1N1 did not lead to sustained improvements in PPE designs or practices. Thus, most US hospitals had great difficulty both developing protocols for Ebola PPE use and training their staff to correctly don and doff PPE.

Participants will serve as their own controls in this pilot study, first in a control arm then a Provodine™ arm. We, the research team, will contaminate participating healthcare workers' (HCW) PPE with either bacteriophage MS2 or *S. marcescens* ATCC 14756. Participants will then doff PPE using the Centers for Disease Control's (CDC) recommended protocol. We will sample their hands using the glove juice method.(124, 125) A research assistant will monitor participants as they wash their hands with soap and water then rinse their hands with 70% ethanol. Participants will then apply Provodine™ to their hands and put on (don) fresh PPE. We will repeat the contamination, doffing, and sampling procedure.

Hypothesis: We hypothesize that Provodine™ will protect participants' hands from contamination with the test contaminants during PPE removal. Bacterial growth from the bag-broth cultures from the Provodine™ arm will have significantly less growth than from the control arm.

1 Background Information and Rationale

1.1 Background Information

Numerous studies have shown that HCWs' knowledge (19, 24, 61, 62) about proper use of PPE and their use of PPE (9, 10, 19, 62-68) are suboptimal. For example, Reid et al. found Canadian pediatric emergency department staff correctly identified the PPE needed for only 1 out of 6 scenarios (24). Casanova et al. noted that ~70% of simulation participants doffed PPE incorrectly despite having access to instructions from the Centers for Disease Control and Prevention (CDC); participants made errors when removing eye protection (33%-56%), N95 respirators (28%-50%), and gowns (17%).(67) In fact, few Canadian HCWs surveyed reported doing hand hygiene after removing various PPE items.(69) Moreover, only 15.4% of HCWs surveyed after the Toronto SARS outbreak reported using safe practices while caring for patients and 22.1% reported using risky practices.(65) Respondents reported being less likely to use appropriate precautions when these precautions were needed most: when caring for sicker patients (APACHE > 20) and when multiple room entries were required.(65) Furthermore, use of PPE varies by item; HCWs are more likely to wear masks, gowns, and gloves than eye protection.(62, 65, 66)

Multiple groups have assessed whether PPE prevents bacterial pathogens from contaminating the environment (70) and HCWs' clothes and bodies.(71-77) These groups demonstrated that HCWs' PPE items are often (9%-69.1%) contaminated with bacterial pathogens, including gram-negative rods (72-77), methicillin-resistant *Staphylococcus aureus* (MRSA) (75), enterococci (72), vancomycin-resistant enterococci (VRE) (73-75), multidrug resistant (MDR) *Pseudomonas aeruginosa* (PA) (76), or MDR *Acinetobacter baumannii* (AB) (76), after caring for patients and that their hands can be contaminated after they remove their gloves (0-12.7%). These investigators estimated that gloves were 77% to 100% effective in preventing hand contamination.(72, 74-76) However, Olsen et al. found glove leaks after 23.7% care episodes and only 21.9% of the participants knew their gloves were breached.(72) Thus, HCWs often contaminate their gowns and gloves while caring for patients with resistant organisms. Furthermore, gloves, while protecting HCWs' hands, are not perfect barriers; results of the laboratory-based study by Doebbeling et al. suggest that even cleansing heavily contaminated gloves before doffing may not protect HCWs' hands from contamination.(71)

During the SARS epidemic (78) and the recent West African Ebola epidemic, HCWs were at high risk of infection.(1, 55) Data from several studies indicate that surgical masks and N95 respirators significantly decreased the risk of SARS infection among HCWs caring for patients with SARS (12, 13, 56) and that inconsistent use of PPE was associated with a higher risk of infection.(16) However, some HCWs who acquired SARS wore appropriate PPE.(18, 79-81) Some of these HCWs may have contaminated themselves during unsafe doffing or during reuse of PPE.(15, 82) Similarly, PPE is an important control measure in Ebola outbreaks (55) but some HCWs who acquired Ebola in West Africa wore PPE appropriately and may have acquired the infection through self-contamination while doffing. Investigators have found similar results for influenza.(57-60, 83-85) Despite evidence supporting PPE use, Chughtai et al. found significant variations in the policies and recommendations around mask and respirator use for protection against influenza and SARS. They postulated that these "differences may reflect the scarcity of level-one evidence.(86)" In the wake of these large and deadly viral epidemics, experts have called for new, improved PPE (87, 88) and for additional robust studies to provide data to guide practice.(89, 90)

Several groups have used fluorescent markers to assess whether HCWs contaminate themselves or the environment when they use or remove PPE.(31, 34, 91-95) Rawson et al. noted that participants' hands became contaminated when they handled the "outside of a contaminated glove" and when gloves "failed.(91)" Moreover, the type of PPE affects contamination levels. Wong et al. found that self-contamination occurred more frequently with jumpsuits than with gowns (92) and Guo et al. found that self- and environmental contamination was more frequent with plastic aprons than with disposable water resistant gowns.(93) Casanova et al. found a high rate of self-contamination (70%-100%) after HCWs doffed PPE contaminated with the bacteriophage MS2, a nonenveloped, nonpathogenic RNA virus.(96) They also found that MS2 was transferred to participants' hands more frequently (78% vs. 23%) and in higher quantity with single-gloving than with double-gloving. Double-gloving did not reduce MS2 contamination

of clothes, possibly because transmission to clothes was related to inadvertent contact with contaminated hands or gowns.(96) Like Zamora et al. (34), they noted that HCWs made more errors while removing PPE when they wore more PPE (double gloves) than when they wore less (single gloves).(67)

1.2 Rationale

We did not identify any studies that assessed whether products applied to the hands could eliminate bacteria or viruses transferred to the hands from contaminated PPE either via defects in the PPE (e.g., holes in gloves) or during improper doffing. Our proposal will test Provodine™, a unique, long-acting Povidine iodine hand rub (113), to determine whether it can eliminate organisms inoculated onto hands through glove defects or by faulty PPE doffing.

Provodine™ has a patented Amidermal® delivery platform, which allows controlled delivery of povidone iodine to the epidermis. In prior laboratory and clinical studies, Provodine™, when applied to the skin, rapidly killed viral (influenza A H1N1, human coronavirus, feline calicivirus) and numerous bacterial pathogens (e.g., *S. aureus*, *Serratia marcescens*) (113) and continued to kill exogenous pathogens inoculated onto treated skin for at least 9 hours. Drs. [name] and [name] recently found that anesthesia providers who performed hand hygiene with Provodine™ before their first case of the day had significantly fewer bacterial colony forming units (CFU) and significantly fewer pathogens, particularly *S. aureus* and *Enterococcus sp.*, on their hands than when they performed hand hygiene with their usual hand hygiene agent (115).

REFERENCES:

3. Fischer WA, 2nd, Hynes NA, Perl TM. Protecting health care workers from Ebola: personal protective equipment is critical but is not enough. Ann Intern Med. 2014;161(10):753-4. Epub 2014/08/27. doi: 10.7326/m14-1953. PubMed PMID: 25155746.

1.3 Risks

The risks to participants are minimal. There is a risk the Provodine™ may cause very mild skin irritation. In addition, there may be other unknown risks, or risks that we did not anticipate, associated with being in this study. Hand cultures collected from participants will be labelled with a study number.

1.4 Benefits

There are no direct benefits to participants from being in this study. However, we hope that, in the future, other people might benefit from this study because this study may help us identify ways to decrease self-contamination while removing personal protective equipment and, thereby, possibly decrease the risk of transmission of infectious diseases from patient to healthcare worker.

1.5 Risk Benefit Ratio

The potential benefits of this study outweigh the minimal risks to participants.

2 Study Objectives, Aims, and Hypothesis

Participants will serve as their own controls in this pilot study, first in a control arm then a Provodine™ arm.

Hypothesis: We hypothesize that Provodine™ will protect participants' hands from contamination with the test contaminants during PPE removal. Bacterial growth from the bag-broth cultures from the Provodine™ arm will have significantly less growth than from the control arm.

3 Study Design and Procedure

Study Design: We will perform a two-armed pilot test among 40 front-line healthcare workers (nurses, doctors, respiratory therapists, etc) at the University of Iowa Hospitals and Clinics. Participants will serve as their own controls. First, participants will perform hand hygiene with alcohol-based hand rub as they normally would in clinical practice then don PPE. We, the research team, will contaminate participating healthcare workers' (HCW) PPE with either bacteriophage MS2 (twenty participants) or *S. marcescens* ATCC 14756 (twenty participants). MS2 preparation and propagation and *S. marcescens* culture suspensions will each be performed as previously described.(123, 124) The MS2 bacteriophage will be suspended in 0.01 M phosphate-buffered saline and each PPE site will be contaminated with 105 plaque-forming units (PFU) of MS2 in 5 drops of 5 µL each. Aliquots of 3 mL of *S. marcescens* broth suspension (yielding bacterial titers of $\sim 1 \times 10^9$ CFU/ml) will be applied to each PPE site. Participants will then doff PPE using the Centers for Disease Control's (CDC) recommended protocol. We will sample their hands using the bag broth method. A research assistant will monitor participants as they wash their hands with soap and water then rinse their hands with 70% ethanol. Participants will then apply Provodine™ to their hands and put on (don) fresh PPE. We will repeat the contamination, doffing, and sampling procedure. For MS2 recovery, we will assay the eluent using the most probable number (MPN) enrichment infectivity assay.(126) For *S. marcescens* recovery, we will dilute the eluent, plate it, incubate the plates, and count the colonies as described.(124, 127)

4 Selection and Withdrawal of Participants

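### Every participant does the control round first and the Provodine round second, so the paired test compares second with first round and cannot isolate the product

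*Combined protocol and SAP*

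**What the plan says.** The Summary and section 2 (Study Objectives, Aims, and Hypothesis) state the same fixed sequence: "first in a control arm then a Provodine™ arm".

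Section 3 (Study Design and Procedure) gives the steps.

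- Round 1: "First, participants will perform hand hygiene with alcohol-based hand rub as they normally would in clinical practice then don PPE". The PPE is then contaminated, doffed by the CDC protocol, and the hands are sampled.
- Between rounds: "A research assistant will monitor participants as they wash their hands with soap and water then rinse their hands with 70% ethanol".
- Round 2: "Participants will then apply Provodine™ to their hands and put on (don) fresh PPE". Then: "We will repeat the contamination, doffing, and sampling procedure".

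Twenty participants are exposed to MS2 and twenty to *S. marcescens*. Each person meets the same organism twice. No randomised order, concurrent control group, practice run or hand sample after the between-round wash is described. Section 5.2 (Informed Consent Process), still in note form, suggests that consent and both rounds take about two hours together. Section 6.2 plans a paired t-test or Wilcoxon signed-rank test on the quantity recovered, with no term for round.

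**The concern.** When every participant has the same order, anything that changes between the first and second attempt is indistinguishable from the product. The protocol itself supplies two candidates that could favour Provodine.

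- **Practice.** Section 1.1 cites a simulation study in which about "70% of simulation participants doffed PPE incorrectly despite having access to instructions". With so many errors there is room to do better at a second attempt, and no practice run comes before round 1.
- **Unequal preparation.** Round 1 follows an alcohol rub alone. Round 2 follows a soap wash, an ethanol rinse and Provodine. The contrast is a bundle, not the product.

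A third effect runs the other way. Organism that survives the wash and rinse would be counted in round 2, against Provodine.

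At stake is the study's only comparison. A significant paired difference would be credited to Provodine although a round effect could produce it, and neither more participants nor a different model could repair this after data collection.

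**Working it through.** **1. The plan's own figure.** Section 6.1 claims 80% power with 20 per organism group for a rate ratio of 0.3 to 0.4. No significance level is stated; 0.05 two-sided is assumed throughout. The unpaired two-proportion formula is

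z = [|p1 − p2|√n − 1.96√(2p̄(1 − p̄))] / √[p1(1 − p1) + p2(1 − p2)].

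For *S. marcescens* at 60% and ratio 0.3, p2 = 0.18 and p̄ = 0.39, so z = (0.42 × 4.472 − 1.96 × 0.690)/0.623 = 0.845 and power is 80.1%. At 70% and ratio 0.4 (28%) it is 77.9%. At 60% and ratio 0.4 (24%) it is 64.5%. For MS2 at 80% and ratio 0.4 (32%) it is 89.5%. The stated figure is thus broadly reproduced. Fixed order does not alter it; it alters what a significant result means.

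**2. What the paired test estimates.** Let τ be the reduction due to the product and π the reduction due to being in round 2 (practice, preparation, residue). For every participant, E(round 1 − round 2) = τ + π. There is one equation and two unknowns, so τ cannot be identified. This step needs no numerical assumption.

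**3. Consequence for the planned t-test.** Set τ = 0 and let π = s, in SDs of the within-person difference. With n = 20, the statistic is noncentral t on 19 df with noncentrality s√20, and the critical value is 2.093.

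| s (assumed) | s√20 | P(significant, favouring Provodine) |
|---|---|---|
| 0 | 0 | 2.5% |
| 0.1 | 0.447 | 6.2% |
| 0.2 | 0.894 | 13.3% |
| 0.3 | 1.342 | 24.6% |
| 0.5 | 2.236 | 56.4% |
| 0.8 | 3.578 | 92.4% |

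**4. The present/absent outcome.** Section 6.1 powers this outcome but section 6.2 names no test for it. Exact two-sided McNemar is assumed: 20 pairs, no product effect, within-person correlation 0 to 0.3. The starting rates are the midpoints of the ranges in section 6.1; the falls are assumptions.

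| Round 1 to round 2 | P(significant, favouring Provodine) |
|---|---|
| 65% to 65% | 0.7% to 1.1% |
| 65% to 60% | 2.0% to 2.4% |
| 65% to 55% | 4.8% |
| 85% to 75% | 3.7% to 4.7% |
| 65% to 45% | 15% to 18% |
| 65% to 35% | 34% to 45% |
| 85% to 60% | 28% to 34% |

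**5. The remedy checked.** With randomised order, E(round 1 − round 2) is τ + π in control-first participants and −τ + π in Provodine-first participants. Half the difference of the two sequence means estimates τ, and π cancels. Its standard error is (σ/2)√(1/10 + 1/10) = σ/√20, the same as for the simple paired test. Only the degrees of freedom fall, from 19 to 18 (critical value 2.101). At a true difference of 0.66 SD, power is 79.7% against 79.9%; at 0.70 SD, 84.1% against 84.4%. In simulation the two-sided type I error stays at 4.9% to 5.0% for round effects of 0, 0.5 and 1.0 SD.

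**The case against.** **The order has a reason.** Section 1.2 says the product "continued to kill exogenous pathogens inoculated onto treated skin for at least 9 hours". Within one day, control-first is the only order that keeps the product out of the control round. This stands, and it rules out reversing the order in one session. It does not defend the lack of a separate day or a parallel control.

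**It is a pilot.** That would carry weight if the aim were feasibility. But sections 2 and 6.1 hypothesise significantly less growth and claim 80% power.

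**Practice is not demonstrated.** The cited error rate shows how often people doff incorrectly, not that they improve on repetition. A reader might infer that the second doffing is supervised or coached; section 3 has the research assistant monitor hand washing only. Practice is plausible but undocumented. With a 10-point fall, the present/absent test gives a false success in no more than 5% of trials.

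**Carry-over is handled.** A reader might infer that organism left from round 1 could create a false success. It could not: residue would raise round-2 counts. The monitored wash and ethanol rinse also reduce it. What remains is a secondary, conservative bias, unmeasured because no sample follows the rinse.

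**A large effect would outrun practice.** The target is a 60% to 70% relative fall. The larger drifts in the second table are smaller: 20/65 = 31%, 25/85 = 29% and 30/65 = 46%. A result of the planned size would exceed them, but the design cannot say how much of it was the round.

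**Conclusion.** The concern holds. Product and round are completely confounded for all 40 participants; that follows from the text alone. A modest round effect of 0.2 to 0.3 SD would raise the chance of a significant result favouring Provodine from 2.5% to 13% to 25% on the planned t-test. On the present/absent outcome the chance is 4% to 5% for a 10-point fall and 15% to 18% for a fall from 65% to 45%.

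These sizes rest on an assumed drift, a two-sided 5% level and, for the t-test, normally distributed differences. That both rounds fall in one session rests partly on the unfinished notes in section 5.2, although the sequence in section 3 points the same way.

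Two stronger readings are not supported. The documents do not show that practice will occur or how large it is, so it cannot be said that the trial will reach a false conclusion. Nor is the direction of the net bias established, since practice and the extra preparation could favour Provodine while residue works against it.

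**What to change.** 1. Randomise the order of the two rounds, 10 control-first and 10 Provodine-first within each organism.
2. Hold the rounds on separate days, because the persistence reported in section 1.2 rules out a same-session reversal.
3. Use the same wash and rinse before both rounds, so that only the final hand product differs.
4. In section 6.2, analyse the paired differences by sequence (half the difference between the sequence means, 18 df per organism).

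The cost is one extra short visit per participant and a 40-line randomisation list. Payment is already tied to completing both arms, and the loss of power is about 0.2 to 0.3 percentage points.

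If a second visit is not possible, add one uninoculated practice don-and-doff before round 1 and give the same wash and rinse before both rounds. This reduces the bias but does not remove it, since the order is still fixed. The conclusion should then be worded as second round versus first round, not as a Provodine effect.

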6.2 Analytical Plan

We will use the paired t-test or Wilcoxon signed-rank test to compare the quantity of MS2 bacteriophage or *S. marcescens* recovered after participants who applied Provodine™ to their hands before donning gloves with the quantity recovered from the control arm where participants who did hand hygiene with an alcohol-based product before donning gloves.

7 Data Collection, Handling, and Storage

All data collected will be stored in an electronic database on a shared drive within the University of Iowa Healthcare servers. Only members of the research team will have access to the database. No PHI will be collected. All participants will be identified in the database by a study number.

We will bank the isolates so that we can do susceptibility testing and pulsed field gel electrophoresis (PFGE) on the isolates in the future if this information is deemed important. All cultures and isolates will be labelled with study numbers and stored in XXXXXXXXX in the [name] lab.

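### A monitored soap wash and ethanol rinse precede only the Provodine run, so the paired contrast is a whole sequence against usual alcohol rub

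*Combined protocol and SAP*

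**What the plan says.** Section 3 (Study Design and Procedure) describes two runs per participant. For the control run the only hand preparation is this: "First, participants will perform hand hygiene with alcohol-based hand rub as they normally would in clinical practice then don PPE". PPE is then contaminated and doffed, and the hands are sampled: "We will sample their hands using the bag broth method".

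The next steps fall between the runs: "A research assistant will monitor participants as they wash their hands with soap and water then rinse their hands with 70% ethanol". Then: "Participants will then apply Provodine™ to their hands and put on (don) fresh PPE". The second run is completed by one sentence: "We will repeat the contamination, doffing, and sampling procedure". Hand preparation is not among the repeated items.

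The Summary gives the same between-run sequence and mentions no hand preparation before the control run. The order is the same for everyone: "first in a control arm then a Provodine™ arm" (Summary and Section 2).

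Section 6.2 compares the quantity recovered after Provodine with the quantity recovered when participants "did hand hygiene with an alcohol-based product before donning gloves". It uses a paired t-test or Wilcoxon signed-rank test, with no term for order or preparation.

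**The concern.** In a within-person comparison, everything except the product should be the same before each donning. Here three things come before the Provodine run and not before the control run: an earlier hand sampling, a monitored soap-and-water wash, and a 70% ethanol rinse. The hypothesis in Section 2 credits any reduction to Provodine alone, and Section 6.2 presents the comparison as one product against another.

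Provodine is meant to act on the skin, and the outcome is organism recovered from that skin. The state of the skin at application is therefore part of the experimental condition. If washing and rinsing change how much organism is transferred or recovered, that change is counted as a Provodine effect, whichever way it goes. The imbalance is total and coincides with run order, so neither the paired test nor a larger sample can separate the two.

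**Working it through.** **Step 1. The plan's own figure.** Section 6.1 states 80% power with 20 participants per organism group and a rate ratio of 0.3 to 0.4. It does not state the test, alpha or sidedness. I assume two-sided 0.05 and an unpaired comparison of two proportions:

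power = Φ{[(p1 − p2)√n − 1.96√(2p̄(1 − p̄))] / √(p1(1 − p1) + p2(1 − p2))}

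- Control 60%, ratio 0.3 (p2 = 0.18): (0.42 × √20 − 1.96 × 0.690)/0.623 = 0.845, so power is 0.801.
- Control 70%, ratio 0.4 (p2 = 0.28): power is 0.779.

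The stated figure is reproduced and is not in dispute here.

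**Step 2. The two preparations side by side (Section 3).**

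| Before donning | Control run (first) | Provodine run (second) |
|---|---|---|
| Earlier contaminated doffing and hand sampling | No | Yes |
| Monitored soap-and-water wash | No | Yes |
| 70% ethanol rinse | No | Yes |
| Alcohol-based rub, usual practice | Yes | None described |
| Provodine | No | Yes |

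Section 6.2 names only the last two rows. With 40 participants, the first three rows apply to 40 of 40 Provodine runs and 0 of 40 control runs.

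**Step 3. What a preparation effect would do to the estimate (illustration).** Let r be the ratio of contamination due to everything in the second-run sequence except the product. Assume it multiplies the Provodine ratio, here taken as 0.5. The documents give no value for either.

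| r | Reported ratio = r × 0.5 | Effect on the Provodine estimate |
|---|---|---|
| 0.8 | 0.40 | Overstated: ln 0.8 / ln 0.40 = 0.24 of the log effect is preparation |
| 1.0 | 0.50 | None |
| 1.2 | 0.60 | Understated: ln 0.60 / ln 0.50 = 0.74 of the true log effect is seen |

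**Step 4. What it could do to the conclusion (illustration).** Section 6.2 names no test for contamination present or absent, so I use exact McNemar, two-sided 0.05, 20 pairs and independent runs. Control rates run from 60% to 90%, as in Section 6.1.

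If Provodine did nothing and r alone acted, the chance of a significant result in its favour would be:

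| r | Chance across control rates 60% to 90% |
|---|---|
| 1.0 | 0.2% to 1.1% |
| 0.9 | 2.8% to 3.6% |
| 0.8 | 6% to 15% |
| 0.6 | 21% to 60% |

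In the other direction, take a true Provodine ratio of 0.4, the upper end of the plan's range. With r = 1.25 the observed ratio is 0.4 × 1.25 = 0.5. On the same calculation, power falls from 50%–93% to 34%–80%.

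In this step r covers preparation and order together, since the design cannot split them.

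**The case against.** The best defence is that the step to "wash their hands with soap and water then rinse their hands with 70% ethanol" is decontamination between runs. It clears first-run organism so that it is not counted in the second, and control hands carry no study organism to clear. That is the natural reading, and it is a good reason to keep the step. It is no reason to leave it out before the control run.

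Second, the marker organism goes onto PPE after donning and is recovered after doffing. A wash before donning may have little effect left by then, and nothing in the documents shows that it does. Alcohol in some form is also used before both runs. These points stand, and they limit how large the bias is likely to be.

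Third, this is a pilot with a deliberate usual-practice comparator. That is a legitimate choice, but the comparison should then be labelled as what it is.

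A reader might infer more than the text supports:

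- **That the extra preparation inflates Provodine's apparent benefit.** The direction is unknown. First-run organism left on the hands would count against Provodine, while practice at doffing would count in its favour.
- **That the control rub is unobserved and adds noise in that arm only.** The text shows the rub is not standardised, but does not say that nobody watches. Provodine application has no stated volume, technique or supervision either, because monitoring is mentioned only for the wash and rinse.
- **That sampling itself physically works the skin.** The documents do not describe how hands are handled during sampling.

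**Conclusion.** The point holds as a mismatch between procedure and stated contrast. Section 3 compares earlier sampling, wash, ethanol rinse and Provodine, always second, with usual alcohol rub, always first. Section 6.2 describes only Provodine against an alcohol-based product.

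The asymmetry is certain, since it rests on the text alone. The size and direction of any bias are not known from the documents. It could be nil or small, and could overstate or understate Provodine. The ratios of 0.8, 1.2 and 1.25 are assumptions chosen to show both directions, not estimates, and the probabilities also rest on the assumed test, alpha and independence of runs. The conclusion that the trial's result would be an artefact of washing is not supported.

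The change is still worth making, because it removes an avoidable difference at little cost using steps the protocol already contains.

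**What to change.** In Section 3, have participants do the same soap-and-water wash and 70% ethanol rinse, monitored by the research assistant, before the control run as before the Provodine run. Then have them apply the arm's product (alcohol rub or Provodine) under the same observation and don PPE. Revise Section 6.2 to describe that contrast.

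The cost is a few minutes and a little soap and ethanol per participant, plus a sentence in each section. The downside is a control run slightly less like routine practice.

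This matches the wash, the rinse and the observation only. Prior sampling, carry-over from the first run and practice at doffing remain tied to the fixed order. Unless order is also balanced across participants, Section 6.2 should state that they remain part of the contrast. If the sponsor prefers to keep the usual-practice control unchanged, the minimum is to reword 6.2 so that it names the full second-run sequence.
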